#### 10.2.3.1 Infections (serious, opportunistic, fungal and Tuberculosis [TB])

- **Incidence of Serious Infection TEAEs per 100 subject years by SOC, HLT and PT**  
Serious infections will be identified based on MedDRA classification (SOC “Infections and infestations”) using the “Any SAE” table. A separate table does not need to be produced to summarize these events.
- **Incidence of Fungal Infection TEAEs per 100 subject years by SOC, HLT and PT**

Fungal infections will be summarized in a stand-alone table. The table will include all TEAEs (serious and non-serious) which code into the High Level Group Term (HLGT) “Fungal infectious disorders”

- **Incidence of Opportunistic Infection TEAEs per 100 subject years by SOC, HLT and PT**

Opportunistic infections (including tuberculosis) will be summarized in a stand-alone table. The table will include all opportunistic infection TEAEs identified using UCB-defined search criteria which were adjudicated as opportunistic infections.

The following steps are followed for identifying and reviewing opportunistic infections:

### **Identification Process**

The two steps below outline two ways in which opportunistic infections (or potential opportunistic infections) can be identified:

Step 1: Refer to column B of the spreadsheet which identifies the Preferred Terms (PTs) to be classified as opportunistic infections using either a single ‘x’ or a double ‘xx’.

- TEAEs which code to a PT flagged with a single ‘x’ need to also be serious to be considered an opportunistic infection.
- All TEAEs which code to a PT flagged with a double ‘xx’ are considered to be an opportunistic infection, regardless of seriousness.

Step 2: Refer to column C of the spreadsheet which identifies the PTs that need to be evaluated on a case-by-case basis by the study physician to determine whether or not it is an opportunistic infection. If Column C has a single ‘x’, then the corresponding preferred term should be flagged for case-by-case review by the study physician.

### **Review Process**

Opportunistic infections for a given study will be reviewed on the following occasions:

- At quarterly Infectious Disease Committee (IDC) Meetings, listings will be produced for each study (see details below) and reviewed by the corresponding study physician ahead of the IDC Meeting. These listings will be posted as part of the broader SSD deliverable to a folder named for the given quarter (eg, 2018Q4) on the SharePoint. They should be based on the same data cut as the one used for SSD and should be delivered at the same time as the SSD outputs. The IDC will then agree on the final adjudication for each potential opportunistic infection.
- For each study, a final listing for opportunistic infections (in the format described below) will be produced and agreed upon between the study physician and the IDC prior to finalizing the database.

In each of the circumstances described above, the study programming team will produce an Excel listing that will be provided to the project lead statistician, project lead programmer, and to the study physician (who will subsequently provide it to the IDC). The Excel listing will contain the following columns (using the descriptions below as the column headings in the Excel listing):

- Study ID

- 
- Unique Subject ID
  - AE Term (Verbatim)
  - AE Preferred Term
  - AE System Organ Class
  - AE High Level Term
  - AE Low Level Term
  - Date of Onset
  - Outcome of Adverse Event
  - Date of Outcome
  - TEAE Flag
  - Serious Adverse Event?
  - Relationship to Study Medication
  - Intensity
  - Action Taken with IMP
  - Opportunistic Infection – Automatic
  - Opportunistic Infection – Manual Review
  - Flag
  - Data Cut Date
  - Opportunistic Infection – Final Adjudication

Note the following about the final 5 variables in this listing:

- *Opportunistic Infection – Automatic*: This is flagged as “Y” if the criteria for automatic selection as described in “Step 1” of the identification process are met.
- *Opportunistic Infection – Manual Review*: This is flagged as “Y” if the criteria for case-by-case selection as described in “Step 2” of the identification process are met.
- *Flag* – This has a value of either “NEW” or “OLD”. It is marked as “NEW” if the event is appearing for the first time in that run of the listing. Otherwise, if it has appeared previously, it is marked as “OLD”. Unique records are determined by USUBJID AESPID for purposes of identifying whether an event has been modified from a previous run.
- *Date* – Only for cases where Flag is “NEW”, this field will be populated with the data cut date for that particular run of the listing.
- *Opportunistic Infection – Final Adjudication* – For new events, this is always left blank by the programmers. It should be completed by the study physician/IDC for every event that appears in the listing. For events adjudicated as opportunistic, the field should be populated with a “Y”.

Following each review by the study physician and IDC, the Opportunistic Infection –Final Adjudication column will be completed (as described above), and the spreadsheets for each study will be returned to the study programming team via e-mail (coordinated by the IDC secretary). Then, for subsequent runs of the listing, the study programming teams will incorporate adjudications from previous runs.

### 10.2.3.2 Malignancies

- **Incidence of Malignant or Unspecified Tumours TEAEs per 100 subject years by SOC, HLT and PT**

These events will be presented in the following tables:

- One table will be based on the criteria (SMQ) = “Malignant or unspecified tumours (SMQ)”
- One table will be based on the criteria SMQ = ”Malignant tumours (SMQ)”.

SMQ search should include all TEAEs which code to a PT included in the Scope=Narrow group within each SMQ.

Note that the events included in the “Malignant tumours” table will be a subset of the events included in the “Malignant or unspecified tumours” table. While the “Malignant tumours (SMQ)” is most relevant, “Malignant or unspecified tumours (SMQ)” must be reviewed for potential malignancies.

The output table will include 2 different overall incidence rows:

- The first overall incidence row will summarize “Any malignancies” and this row will summarize the incidence of all AEs flagged for inclusion in the table (using the appropriate SMQ depending on the table), regardless of the High Level Term (HLT) it codes to
- The second overall incidence row will summarize “Any malignancy excluding non-melanomic skin cancers HLT” and this row will summarize the incidence of AEs flagged for inclusion in the table (using the appropriate SMQ depending on the table), excluding those which code to an HLT of “skin neoplasms malignant and unspecified (excl melanoma)”.

### 10.2.3.3 Cardiac events

- **Incidence of Major Adverse Cardiac Event (MACE) TEAEs per 100 subject years by SOC, HLT and PT**

Potential cardiovascular events are adjudicated by the independent Cardiovascular Event Adjudication Committee (CV-CAC) according to the CV-CAC Charter (version 6.0). Adjudicated events are classified by the CV-CAC to one of the event types as defined in the cardiovascular event classifications Table below. The classification of an event as a Major Adverse Cardiac Event (MACE) is also determined by the CV-CAC. Events which are classified by the CV-CAC as any of the event types identified in the third column of the table will be considered an extended MACE. Note that extended MACE is determined programmatically and includes a broader scope definition of MACE.

MACE as determined by the CV-CAC will be presented in a table and listing. Extended MACE will be presented separately in a table and listing. Additional listings of all MACE as determined by the CV-CAC will be presented separately for the OLE and the OLE2 treatment periods.

Another table and listing will present the adjudicated cardiovascular events by type. For each cardiovascular event type, the individual PTs which fall within each event type will be summarized. This listing will indicate whether each event was determined to be a MACE and/or an extended MACE. Similar listings of the adjudicated cardiovascular events by type will be presented separately for the OLE and the OLE2 treatment periods.

Additionally, a listing of all events identified for potential review by the CV-CAC will be produced. This listing will indicate whether each event was identified by the CV-CAC Chair for full committee review. Similar listings of all events identified for potential review by the CV-CAC will be produced separately for the OLE and the OLE2 treatment periods.

### Cardiovascular event classifications

Event Type Code	Event Type	Extended MACE
1	Non-Fatal Myocardial Infarction (MI)	Yes
2	Non-Fatal Stroke: hemorrhagic	Yes
3	Non-Fatal Stroke: ischemic	Yes
4	Non-Fatal Stroke: embolic	Yes
5	Non-Fatal Stroke: undeterminable	Yes
6	Hospitalization or ER for Unstable Angina with urgent revascularization	Yes
7	Hospitalization or ER for Unstable Angina without urgent revascularization	No
8	Hospitalization for Heart Failure	Yes
9	Transient Ischemic Attack (TIA)	No
10	Coronary Revascularization Procedures (e.g. percutaneous coronary intervention, coronary artery bypass grafting)	Yes
11	Urgent Revascularization Procedures (i.e. due to symptoms of brain ischemia or pending infarction)	Yes
12	Arrhythmia (not associated with ischemia)	No
13	Peripheral Arterial Event	No
14	Venous Thromboembolic Event: pulmonary embolism (PE)	No
15	Venous Thromboembolic Event: deep vein thrombosis (DVT)	No
16	Venous Thromboembolic Event: PE and DVT	No

### Cardiovascular event classifications

Event Type Code	Event Type	Extended MACE
17	Other CV Event	No
18	Death due to Myocardial Infarction (MI)	Yes
19	Death due to Stroke	Yes
20	Sudden Cardiac Death	Yes
21	Other CV Death (e.g. heart failure, pulmonary embolism, cardiovascular procedure-related)	Yes
22	Cardiovascular: Undetermined Cause of Death (i.e. cause of death unknown)	Yes
23	Non-Cardiovascular Death	No
24	Non-Cardiovascular Event	No
99	Inadequate information to adjudicate	No

CV=Cardiovascular; DVT=Deep Vein Thrombosis; ER=Emergency Room; MACE=Major Adverse Cardiac Event; MI=Myocardial Infarction; PE=Pulmonary Embolism; TIA=Transient Ischemic Attack.

MACE is determined by the adjudication committee and is not identified programmatically based on event type.

#### 10.2.3.4 Neutropenia

- **Incidence of Neutropenia TEAEs per 100 subject years by SOC, HLT and PT**

A table based on the following PTs (regardless of seriousness) will be produced:

- Autoimmune neutropenia
- Band neutrophil count decreased
- Cyclic neutropenia
- Febrile neutropenia
- Idiopathic neutropenia
- Neutropenia
- Neutropenic infection
- Neutropenic sepsis
- Neutrophil count decreased

#### 10.2.3.5 Suicidal Ideation and Behavior (SIB)

- **Incidence of SIB-Adjudicated Neuropsychiatric TEAEs per 100 subject years by SOC, HLT and PT**

Potential neuropsychiatric events are adjudicated by the independent Neuropsychiatric Adjudication Committee according to the Neuropsychiatric Adjudication Committee (version 8.0). Adjudicated events are classified by the Committee as Suicidal or Non-suicidal. Adjudicated events are also further classified by the Committee to one of the event types as defined in neuropsychiatric event classifications Table below. Suicidal Ideation and Behavior (SIB) is defined as events classified by the Committee as Suicidal.

A table and listing will present SIB events. This listing will also be provided separately for OLE and OLE2 treatment periods.

Another table and listing will present the adjudicated neuropsychiatric events by type. For each neuropsychiatric event type, the individual PTs which fall within each event type will be summarized. This listing will indicate whether each event was determined to be Suicidal or Non-Suicidal. For event type suicidal ideation, the listing will also indicate if intent was present and if the suicidal ideation was clinically significant. A similar listing of the adjudicated neuropsychiatric events by type will be presented.

Additionally, a listing of all events identified for potential review by the Committee will be produced. This listing will indicate whether each event was identified by the Neuropsychiatric Event Adjudication Committee Chair for full committee review. Similar listings will be provided separately for the OLE and the OLE2 treatment periods.

### Neuropsychiatric event classifications

Event Type Code	Event Classification	Event Type
1	Suicidal	Suicidal events/completed suicide
2	Suicidal	Suicide attempt
3	Suicidal	Preparatory acts toward imminent suicidal behavior
4	Suicidal/Non-suicidal a	Suicidal ideation
7	Non-suicidal	Nonsuicidal Self-injurious behavior
8	Non-suicidal	Nonsuicidal Other
99	Not applicable	Inadequate information to adjudicate

Suicidal ideation event types can be classified by the Neuropsychiatric Adjudication Committee as Suicidal or Non-suicidal depending on whether intent to die was present

#### 10.2.3.6 Inflammatory bowel disease

- **Incidence of Inflammatory Bowel Disease TEAEs per 100 subject years by SOC, HLT and PT**

Selected gastrointestinal events are adjudicated by the independent Inflammatory Bowel Disease (IBD) Adjudication Committee (IBD-CAC) according to the IBD-CAC Charter (version 3.0). Adjudicated events are classified by the IBD-CAC into one of the diagnostic types as defined in

the IBD event classifications Table below. The events will further be classified as definite, probable or possible IBD.

An overview of adjudicated IBD events will be stratified by subjects with or without a previous medical history of IBD. Previous medical history of IBD will be determined using the information recorded on the Extra-Articular Assessment at Screening CRF page ("Does subject have a history of IBD?"). This overview table will present events adjudicated by the IBD-CAC as either possible, probable or definite IBD. Definite and probable IBD will also be aggregated and summarized in this table. In addition, this table will summarize each IBD event classification (possible, probable or definite) separately.

Another table and listing will present the adjudicated IBD events by type. For each IBD event type, the individual PTs which fall within each event type will be summarized. Similar listings of the adjudicated IBD events by type will be presented separately for OLE and OLE2 treatment periods.

Additionally, a listing of all events identified for potential review by the IBD-CAC will be produced. This listing will indicate whether each event was identified by the IBD-CAC Chair for full committee review. Similar listings of all events identified for potential review by the IBD-CAC Chair for full committee review will be produced separately for the OLE and the OLE2 treatment periods.

A further supportive listing will present the individual diagnostic criteria met for each adjudicated IBD event. This listing will also be presented separately for the OLE and the OLE2 treatment periods combined.

### IBD event classifications

Event Type Code	Event Type (Classification and diagnosis)	Classification
1	Possible Inflammatory Bowel Disease – Crohn’s Disease	Possible
2	Probable Inflammatory Bowel Disease – Crohn’s Disease	Probable
3	Definite Inflammatory Bowel Disease – Crohn’s Disease	Definite
4	Possible Inflammatory Bowel Disease – Ulcerative Colitis	Possible
5	Probable Inflammatory Bowel Disease – Ulcerative Colitis	Probable
6	Definite Inflammatory Bowel Disease – Ulcerative Colitis	Definite
7	Possible Inflammatory Bowel Disease – type unclassified	Possible
8	Probable Inflammatory Bowel Disease – type unclassified	Probable
9	Definite Inflammatory Bowel Disease – type unclassified	Definite
10	Symptoms not consistent with Inflammatory Bowel Disease	Not applicable
11	Possible Inflammatory Bowel Disease – Microscopic Colitis	Possible
12	Probable Inflammatory Bowel Disease – Microscopic Colitis	Probable

### IBD event classifications

Event Type Code	Event Type (Classification and diagnosis)	Classification
13	Definite Inflammatory Bowel Disease – Microscopic Colitis	Definite
14	Possible Inflammatory Bowel Disease – no further differentiation possible	Possible
15	Probable Inflammatory Bowel Disease – no further differentiation possible	Probable
16	Definite Inflammatory Bowel Disease – no further differentiation possible	Definite
99	Not enough information to adjudicate	Not applicable

IBD=inflammatory bowel disease.

Note: IBD diagnoses of “microscopic colitis” and “no further differentiation possible” were added in an adjudication charter amendment, accounting for the event type numbering.

#### 10.2.3.7 Hypersensitivity (including anaphylaxis)

- **Incidence of Anaphylactic Reaction TEAEs per 100 subject years by SOC, HLT and PT**

A separate table will be prepared based on the MedDRA anaphylaxis Algorithm (see Appendix A) for acute anaphylactic events (reported on the same day as when an injection was administered or one day after). An AE glossary table will also be produced to summarize the MedDRA coding for these events. The glossary table will include the following fields: reported term, PT, LLT, HLT, and SOC.

A separate table will be prepared to summarize hypersensitivity events, identified using the SMQ “Hypersensitivity (SMQ)”. All TEAEs which code to a PT included in the Scope=Narrow search will be included in this table. In addition, a separate table will be prepared to summarize serious hypersensitivity events, identified using the SMQ “Hypersensitivity (SMQ)”. All serious TEAEs which code to a PT included in the Scope=Narrow search will be included in this table. An AE glossary table will also be produced to summarize the MedDRA coding for these events. The glossary table will include the following fields: reported term, PT, LLT, HLT, and SOC.

Furthermore, a separate table will be prepared to summarize injection site reactions, identified using the HLTs: “Administration site reactions NEC” and “Injection site reactions”.

#### 10.2.3.8 Hepatic events

- **Incidence of hepatic events TEAEs per 100 subject years by SOC, HLT and PT**

A table for hepatic events will be created based on the SMQ of “Drug related hepatic disorders - comprehensive search (SMQ)”. However, these 2 sub-SMQs are to be excluded: “Liver neoplasms, benign (incl cysts and polyps) (SMQ)” and “Liver neoplasms, malignant and unspecified (SMQ)”. For each of the above SMQs, include all TEAEs which code to a PT included in the Scope=Broad and/or Scope=Narrow.

Note that all AEs meeting the above criteria are to be included. It should not be limited to events that the investigator determined to be related to study drug.

Cases of Hy's Law will be reported separately in a liver function test table.

A by-subject listing of all AEs of safety topics of interest by type of safety topics of interest will be provided.

### 10.3 Clinical laboratory evaluations

If not specified otherwise, laboratory values, including markedly abnormal laboratory values will be presented descriptively by treatment group for the SS. Tables presenting markedly abnormal values and those based on CTCAE grade only include selected laboratory variables.

For tables where data are summarized by visit, unscheduled and repeat visits will not be summarized, but these data will be included in listings. For tables where multiple measurements over a period of time are considered (as in shift tables), unscheduled and repeat visits will be considered as long as they were collected in the period being summarized. All summaries will be presented in SI units and will be based on observed case values. In the case where laboratory values are below the lower limit of quantification, then these will be set to the midpoint between 0 and the lower limit of quantification for the purpose of summarizing the data. The following summaries are required:

- A summary of observed results and change from Baseline values in each laboratory variable by treatment group and visit
- A summary of the number and percentage of subjects experiencing markedly abnormal values at any time while on treatment (assessment on or following the first dose of study treatment through the final dose of study treatment + 140 days) by laboratory variable and treatment group. Two separate tables will show results for the initial treatment period (for the SS) and the Initial and Maintenance Treatment Period (for the MS). An additional table for the OLE period will be provided for the OLS by treatment the subjects were receiving at the time of the assessment of the abnormal value.
- A summary of the number and percentage of subjects with a given CTCAE grade (0, 1, 2, 3, or 4) based on minimum/maximum post-baseline value by laboratory variable and treatment group. Two separate tables will show results for the initial treatment period (for the SS) and the Initial and Maintenance Treatment Period (for the MS). An additional table for the OLE period will be provided for the OLS by treatment the subjects were receiving at the time of the assessment of the value with the given CTCAE grade.
- A shift table of the number and percentage of subjects experiencing CTCAE grade 0, 1, 2, 3, or 4 values (as applicable) at Baseline to minimum/maximum post-Baseline CTCAE grade, by laboratory variable and treatment group. Two separate tables will show results for the initial treatment period (for the SS) and the Initial and Maintenance Treatment Period (for the MS). An additional table for the OLE period will be provided for the OLS by treatment the subjects were receiving at the time of the assessment of the value with the given CTCAE grade. A lipid profile table of treatment emergent markedly abnormal laboratory data will be provided for the Initial and Maintenance Treatment Period (SS) and the Open-label Extension treatment period (OLS) separately.

In addition, a shift table of number and percentage of subjects experiencing post-Baseline HDL Low risk ( $\geq 1.55$  mmol/L), Intermediate risk ( $\geq 1.04 - < 1.55$  mmol/L) and High risk ( $< 1.04$  mmol/L) compared to baseline will be provided for the Initial and Maintenance Treatment Period (SS) and the Open-Label Extension Treatment Period (OLS).

Shift laboratory summaries will use the Baseline for Open-Label Extension Period for subjects switching from secukinumab to Bimekizumab as described in Section 3.2.

A figure of neutrophil values over time for subjects with at least one markedly abnormal neutrophil value (CTCAE Grade 3 or 4) will also be presented.

A by-subject listing of all laboratory data (including urinalysis) will be provided. Separate by-subject listings for the OLE and the OLE2 treatment periods will be provided. These listings will be presented by treatment group and will include: center, subject identifier, age, sex, race, weight, visit, laboratory variable, result (with abnormal values flagged as “L” or “H” accordingly) and unit.

Markedly abnormal values are defined as those with a severity of Grade 3 and above based on the common terminology criteria for adverse events (CTCAE) criteria (U.S. Department of Health and Human Services 2010). Definitions of markedly abnormal values using the Grade 3 cut points are given in the tables below for age ranges of  $\geq 17$  years (Table 10–1 for markedly abnormal liver function test values, Table 10–2 for markedly abnormal biochemistry values and Table 10–3 for markedly abnormal hematology values). Tables summarizing markedly abnormal values should include a summary (counts and percentages) of markedly abnormal labs observed at any time while on treatment (ie, treatment-emergent markedly abnormal [TEMA]). For this summary, Baseline values and values observed more than 140 days after the last administration of study medication are not considered. The laboratory results classified as Grade 3 or Grade 4 will be summarized and listed separately.

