#### **3.5.3 Safety Set**

The Safety Set (SS) will consist of all subjects that received at least 1 dose of IMP.

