#### **3.5.5 Maintenance Set**

The Maintenance Set (MS) will consist of all subjects that receive at least 1 dose of IMP at Week 16 or later in the double-blind Treatment Period (including the Week 16 dose).

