## 10 SAFETY ANALYSES

If not specified otherwise, all safety summaries and listings will be created using all subjects in the SS.

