### 10.1.3 Exposure during the Initial and Maintenance Treatment Period for SS

Definitions for study medication duration (days) and time at risk (days) during the Initial and Maintenance Treatment Period are provided as follows:

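### Three laboratory safety tables covering Weeks 0 to 48 are set on the Maintenance Set, so treated subjects who stopped before Week 16 are left out of them

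*SAP*

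**What the plan says.** Section 10 sets the general rule that, unless otherwise specified, "all safety summaries and listings will be created using all subjects in the SS". Section 10.3 repeats it for laboratory data: "If not specified otherwise, laboratory values, including markedly abnormal laboratory values will be presented descriptively by treatment group for the SS".

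Three bullets of section 10.3 then depart from it. They cover markedly abnormal values, the CTCAE grade based on the most extreme post-Baseline value, and the CTCAE shift from Baseline. Each contains the sentence "Two separate tables will show results for the initial treatment period (for the SS) and the Initial and Maintenance Treatment Period (for the MS". The shift-table bullet ends with a further table on a different population: "A lipid profile table of treatment emergent markedly abnormal laboratory data will be provided for the Initial and Maintenance Treatment Period (SS".

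The two sets are defined in section 3.5. For the Safety Set (SS): "The Safety Set (SS) will consist of all subjects that received at least 1 dose of IMP". For the Maintenance Set (MS): "The Maintenance Set (MS) will consist of all subjects that receive at least 1 dose of IMP at Week 16 or later" in the double-blind period. The on-treatment window for markedly abnormal values starts at the first dose: "assessment on or following the first dose of study treatment through the final dose of study treatment + 140 days".

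**The concern.** The period and the population do not match. A table for the combined Initial and Maintenance Treatment Period covers time from the first dose. The MS admits only subjects who were still being dosed at Week 16.

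Membership of the MS is decided after treatment starts, and the toxicity being tabulated can decide it. A subject whose Grade 3 or 4 value leads to stopping at Week 8 contributes nothing to the combined-period table. What is at stake is whether the three 48-week laboratory displays describe everyone treated, and whether they can be read against the 16-week laboratory tables and the combined-period adverse event tables, both of which are on the SS.

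**Working it through.** The SAP states no figure here to reproduce. The check compares the named populations and then gauges the size under assumed counts.

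**Step 1. Population named for the combined period elsewhere in the SAP**

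| Output | Section | Set |
|---|---|---|
| Exposure ("Exposure during the Initial and Maintenance Treatment Period for SS") | 10.1.3 | SS |
| Adverse events | 10.2.2 | SS |
| Safety topics of interest | 10.2.3 | SS |
| Lipid markedly abnormal values, HDL shift | 10.3 | SS |
| Blood pressure shift, markedly abnormal vital signs | 10.4.1 | SS |
| ECG | 10.4.3 | SS |
| Markedly abnormal labs, CTCAE grade, CTCAE shift | 10.3 | **MS** |

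Elsewhere in the safety sections the MS is paired with the Maintenance Treatment Period alone: exposure (10.1.2), adverse events (10.2.2), hypersensitivity and hepatic events (10.2.3). No reason is given for the exception in section 10.3. The lipid parameters also stand in the general list of markedly abnormal values (Table 10–2). If they are among the variables selected for the general table, the same result for the same period is reported on two populations.

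**Step 2. Effect on the rate**

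Let N be the number treated in an arm, k the number stopping before Week 16, T the number ever affected in the double-blind period, and e the number affected among the k.

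- SS rate = T / N
- MS rate = (T − e) / (N − k)
- The MS rate is the lower one exactly when e / k > T / N, that is, when early stoppers are affected more often than the arm as a whole.

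Inputs: N = 350 (planned per arm, section 2.3.2.2). T = 10, e = 0, 2 or 5, and early stopping of 2%, 5% or 10% are assumptions. Section 4.2.1 says only that discontinuation before Week 16 should be low. The three rates give k = 7, 18 (17.5 rounded) and 35.

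| Early stopping | N − k | e = 0 | e = 2 | e = 5 | SS rate |
|---|---|---|---|---|---|
| 2% | 343 | 10/343 = 2.9% | 8/343 = 2.3% | 5/343 = 1.5% | 10/350 = 2.9% |
| 5% | 332 | 10/332 = 3.0% | 8/332 = 2.4% | 5/332 = 1.5% | 10/350 = 2.9% |
| 10% | 315 | 10/315 = 3.2% | 8/315 = 2.5% | 5/315 = 1.6% | 10/350 = 2.9% |

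The lost cases move the rate much more than the smaller denominator does. At 5% stopping the threshold is e > 18 × 10/350 = 0.51, so one affected early stopper is enough to lower the rate.

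**Step 3. The 48-week count against the 16-week count**

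Let A be the number affected in the Initial Period SS table, e those of them who stop before Week 16, and L the MS subjects first affected later. The combined-period MS count is A − e + L, which is below A whenever e > L. Assumed example: A = 7, e = 5, L = 3 gives 7 − 5 + 3 = 5. The longer period then shows 5 affected subjects and the shorter one 7, which cannot happen on a common population.

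**The case against.** The best defence is that these subjects are not lost from the report. The same three displays are produced for the Initial Treatment Period on the SS, which is when they were treated. The combined-period lipid and HDL tables are on the SS. The AST/ALT threshold table, the potential Hy's Law and pDILI tables, the AST and ALT plots and the neutrophil figure carry no MS restriction, so the SS default applies. Neutropenia and hepatic adverse events are tabulated on the SS for the combined period, as are adverse events leading to discontinuation. All laboratory data are listed by subject. This stands, and it limits the point to three descriptive tables.

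Three stronger readings are tempting, and the SAP does not support them:

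- **That toxicity leading to stopping is hidden from the 48-week laboratory results.** The outputs just listed show it, and neutrophils and transaminases are among the best covered.
- **That the rates are biased low as a matter of fact.** This is conditional. If no affected subject stopped early, the MS rate is the same or slightly higher (10/332 = 3.0% against 10/350 = 2.9%). Toxicity-related stopping is plausible, but no figure in the SAP establishes it.
- **That some values fall in neither table.** Adverse events and eC-SSRS events after Day 112 in early discontinuers are excluded from the Initial Period outputs. If laboratory values were cut in the same way, a late value in such a subject would be in neither laboratory table. The SAP does not state that cut for laboratory data.

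None of this gives a reason for using the MS in a table that begins at the first dose.

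**Conclusion.** The three combined-period laboratory tables are assigned to the wrong population as written, against the SAP's own default and its practice for the same period. That conclusion rests only on the set definitions.

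The size cannot be fixed from the SAP. Under the assumed counts, the combined-period rate moves from 2.9% to between 1.5% and 3.2%. The direction is downward only if affected subjects stop early more often than others. Since early discontinuation is expected to be low, few subjects are probably involved.

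No hypothesis test, efficacy estimate or secondary safety variable is touched: the secondary safety variables are exposure-adjusted adverse events, and their combined-period summaries use the SS. The point should be corrected, but it does not threaten the trial's main conclusions.

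**What to change.** In all three bullets of section 10.3, name the SS instead of the MS for the combined Initial and Maintenance Treatment Period.

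Add one sentence on columns. Bimekizumab subjects who stopped before re-randomization are counted under the treatment they received (320mg Q4W) and in the bimekizumab total. A footnote should say that the Q4W column then holds all bimekizumab early stoppers, so Q4W and Q8W are not compared as randomized groups in these tables.

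If a Maintenance-only view is wanted, add it as a separate table on the MS, labelled for that period.

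The cost is the SAP wording, a changed population flag and a rerun of three tables; no new data are needed. This SAP version was written after the Week 48 interim analysis (section 9 refers to that summary in the past tense), so the change should be recorded as made after it. If the Week 48 tables were produced on the MS, the report should say so and show both versions.
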